This could in particular be effective because the proposed populationbased screening study focuses on the group with the highest risk, for whom, at the same time, the effectiveness of the mammography is the most limited. The intended effect on a national level is as follows: Every year, there are about 900,000 women in the Netherlands between the age of 50 and 75 who are screened using mammography as part of the Dutch population-based mammography screening program. About 5% of these women have extremely dense breasts (>75% density), so 45,000 women. It is expected that adding an MRI to the mammography screening in this high-risk group will decrease the number of interval cancers from 4.4 per 1000 screened women to 1.44 per 1000 screened women (1;6) (calculations are explained further in section 7.7). On a national level, this means that the number of interval cancers per screening round in this group decreases from 199 to 65. The prognosis of patients with tumours discovered through screening is better than that of patients with interval cancers, with an estimated 5-year survival rate of 95% and 78% respectively (2). On the basis of these figures, we estimate that 23 deaths due to breast cancer could be prevented per screening round: 134 tumours (199 minus 65) detected now through screening instead of in the interval, and of which as a result thereof, 17% fewer breast cancer deaths in 5 years (95% minus 78%). From previous research in the screening population of 50-70 years, we know that the average age of women with >75% density is around 53 years. If we calculate with an average life expectancy of another 27 years, an additional 621 extra life years are gained per round with the proposed population-based screening study. In addition, this population-based screening study will have a favourable effect on the quality of life of breast cancer patients, considering a large part of the interval cancers (67%) will be diagnosed sooner through screening, which means an aggressive treatment will be required less frequently. 3. Natural course of the disease About 13,000 women in the Netherlands are diagnosed with breast cancer annually (Source: www.ikcnet.nl 2009). Three guarters of these women are 50 years or older (± 9,750). Important predictive factors for the prognosis of breast cancer are tumour diameter, axillary lymph node status and histologic tumour grade (1;15). In the Netherlands, women between the age of 50 and 75 are screened every two years using mammography as part of the Dutch population-based mammography screening program. The population-based screening program detects about 5,000 breast tumours each year (51% of all tumours among women older than 50) (1). However, not all tumours are detected through the population-based screening program: Among the participants, about 30% of the tumours are discovered in the interval between the screening rounds (the so-called interval cancers) (1). This large number of interval cancers is a problem since the staging, and with that the prognosis, is less favourable compared to the

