The harms primarily consist of false-positive MRI results and, as a result, further follow-up and possible interventions which turned out to be unnecessary. This could create stress and loss of trust.

3. Ratio

By selecting the group of women with the highest breast density, , MRI examination will take place in a group of women that will benefit from it the most, because of their high risk and very limited mammography value. The

		harm is determined by the sensitivity of MRI in this hand, and the number of false positives on the other	
Part 7. Medical-scientific research project description (max. 525 lines)			
	1. Projectleader		
	Name contact perso	n: [name] [name]	
	position:	Associate [name]	
	institution:	Julius Center for Health Sciences and Primary Care, UMC Utrecht	
	correspondence add	lress: [name]	
	postcode:	[name]	
	city:	Utrecht	
	[contact]	
	telefax:	[name]	
	2. Problem definition	on	
	fibroglandular and s breast cancer than w the sensitivity of mar (4-8), so in this group interval cancer com cancers are tumours example, because a	dense breast tissue (>75% of the breast consists of stromal tissue) are 4-6 times more likely to develop women with little or no dense tissue (3). On top of that, mmographic screening is very limited with these women p of women, breast cancer presents itself more often as apared to the group with low breast density. Interval is that show itself in between two screening rounds; for a woman has complaints. In general, interval cancers posis than tumours detected through screening.	
	population-based so method that has a r	he highest risk at developing breast cancer in the creening program are momentarily screened using a nerely limited value for them, and they could probably ore sensitive screening methods, such as MRI.	
	3. Objective		
	women who particip	detect more breast tumours in an earlier stage among bate in the population-based mammography screening have very dense breasts, eventually to reduce the ncer deaths.	

4. Research question
 What is the effectiveness of screening every 2 years using mammography combined with MRI compared to mammography only in reducing the number of interval cancers (as proxy for breast cancer mortality) among women with extremely dense breasts? What is the cost-effectiveness of each of these strategies? What is the influence of the MRI examination on the quality of life of the participating women? What is the degree of participation to the MRI study?

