screening trial results such as these, and to compare the cost-effectiveness of different screening measures (38;39). It is a validated model that has been applied numerous of times successfully in evaluating different screening strategies. It is also one of the most commonly used breast cancer models by the Cancer Intervention and Surveillance Modelling Network (CISNET) consortium sponsored by the National Cancer Institute (40). In MISCAN, the individual life courses are generated as a Markov process of stages and transitions. For this, the characteristics of the study population (demographic data, risk factors) are fed to the model. The results of the screening and the scenarios as applied in the proposed experimental population-based screening study are estimated for a cohort of 1 million women with very dense breasts. The effects on mortality and life vears gained with the different screening scenarios are estimated at a period of 10 years after the start of the screening. The most important parameters in the model are the average duration of the preclinical stages that can be detected with screening, sensitivity of the screening test and improvement in prognosis after detection through screening. Outcomes of the model are the number of screen-detected tumours and interval cancers (including stage distribution), age-specific breast cancer incidence, stratified by stage, and age-specific breast cancer mortality.

Analysis of cost-effectiveness

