The breast cancer simulation model will also be used to predict the costs and effects of different screening strategies for a situation in which the screening is carried out for 10 years. The costs of the diagnosis and treatment of breast cancer will be registered as part of the experimental population-based screening study. Costs and effects are calculated for a simulated cohort of 1 million women for a period of 10 years after the start of the screening. The costs are presented in euros. The effects are presented in terms of breast cancer mortality reduction and number of life years gained. Cost-effectiveness ratios (CER) are expressed in costs per life-year gained and incremental cost-effectiveness ratios (ICER) as extra costs per extra life-year gained. For the intervention group, the guality of life is assessed using the EuroQoI-5D questionnaire. To estimate the number of guality-adjusted life years of the control group, we use the EuroQol-5D health status data of the general population of Dutch women of the age between 50 and 75 (41). We implement weighting factors with a reduction of 10%, 25%, 40% for respectively non-metastatic tumours, tumours with metastases in the regional lymph nodes or tumours with distant metastases. For this reason, the ICER is expressed in extra costs per quality adjusted life-year gained.

Analysis of quality of life

The effect of MRI screening on the quality of life of the women will be assessed using questionnaires. The EuroQoI-5D questionnaire is a validated and a frequently-used questionnaire that is able to assess the quality of life with a few short questions, regarding physical as well as psychological consequences (41).

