In addition, the psychological consequences the experimental populationbased screening study could cause will also get attention by using the 'Consequences of Screening---Breast Cancer' (COS-BC) questionnaire (42). The first part of the questionnaire (COS-BC-1) asks specifically about the fears and uncertainties during the screening procedure. The second part of the questionnaire (COS-BC-2) aims to get the woman to look back at the entire period of examinations and have her assess whether it has brought about positive and/or negative changes. The great advantage of the COS-BC questionnaire in comparison to other validated anxiety questionnaires is the fact that it is focussed specifically on breast cancer screening. With three short questions, the screen-specific items questionnaire uncover the burden experienced by the MRI examination (43). The group of women with MRI-detected breast cancer will be asked to answer the EORTC questionnaire once (44). The goal of the quality of life analysis is to investigate the (changing) quality of life in the intervention arm as a whole. Besides, whether differences can be observed between participants with false positive, true positive, false negative and true negative MRI results will be addressed. The moments at which time the different questionnaires are conducted is indicated in the flowchart (see 'Flowchart timing of questionnaires'). Interim analyses The first analyses are carried out after the first screening round, namely: 1. When all women in the intervention group have received an MRI, including any possible diagnostic work-up. At that point, the extra number of tumours detected by the MRI, and missed by the mammography, can be estimated, as well as the recall rate, the positive predictive value and the number of biopsies per positive MRI test. 2. Two years after the last participant has been screened, the difference in the proportion of interval cancers is analysed and the tumour size and stage between both groups are compared. An interim analysis on the primary outcome is not possible, because information on interval cancers is only available after all participants have been screened and followed for two years. For the false-positive percentage, interim monitoring will take place. From the abstract from Berg et al. (23) on the added value of MRI in the ACRIN 6666 trial, it is possible to calculate that the percentage 'unjustified' referrals in the entire investigated group is 17% and the percentage 'unjustified' biopsies is 9%. Based on this, we have decided the following: If after the first 750 MRI examinations the number of unjustified referrals is more than 25% or the number of unjustified biopsies is above 15%, consultation on modification of the intervention in relation to the referral criteria is necessary and suspending the trial could be considered. A Data Safety and Monitoring Board is installed to this end, in any case consisting of an independent biostatistician, radiologist and oncologist as its members.

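### The cost-per-QALY analysis takes EQ-5D from the trial for the MRI arm but from population data for controls, so differences between the sources can pass as an MRI effect

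*Combined protocol and SAP*

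**What the plan says.** Cost-effectiveness is the second research question (Part 7, section 4). Under Analysis of cost-effectiveness (Part 7, section 9), the two arms get their quality-of-life input from different places:

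- Arm I: "For the intervention group, the guality of life is assessed using the" EuroQol-5D.
- Arm II: QALYs rest on EuroQol-5D "health status data of the general population of Dutch women of the age between 50 and 75". Nothing is measured in the controls themselves. Part 7, section 6 limits control data to cancer occurrence and breast cancer mortality from record linkage.

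Utility reductions of 10%, 25% and 40% are then applied by tumour spread, and "the ICER is expressed in extra costs per quality adjusted life-year gained". A cost per life-year gained is also planned. The model is a simulation of 1 million women with very dense breasts, whose effects "are estimated at a period of 10 years after the start of the screening" (Estimation of mortality reduction).

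On who answers in arm I, the text points two ways. The research question reads "What is the influence of the MRI examination on the quality of life of the participating women", while Analysis of quality of life sets out to "investigate the (changing) quality of life in the intervention arm as a whole". The flowchart of questionnaire timing is not reproduced in the public text.

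**The concern.** An incremental QALY is a subtraction, and here its two terms come from different populations. Three features make it likely that the populations differ for reasons unrelated to MRI.

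- **Eligibility for MRI.** Randomisation depends only on density and a negative mammogram. MRI contraindications (Part 7, section 6) and severe kidney dysfunction (the contrast-risk text ahead of Part 7, section 12) then act in arm I alone. The population values carry no such restriction.
- **Willingness.** Participation is expected to be 66% (Part 7, section 7). Women who decline only unregister, with the option of giving a reason (Part 7, section 12). No visible text describes sending them EQ-5D.
- **Age.** Part 2, section 2 says "we know that the average age of women with >75% density is around 53 years". The control values cover ages 50 to 75, and no matching or standardisation is stated.

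The plan's safeguards do not reach this comparison. The intention-to-treat rule is given in the sample-size section for participation in MRI, and the non-compliance adjustment in section 9 is given for the screening effect. Neither is extended to EQ-5D. At stake is whether the reported cost per QALY reflects MRI or the choice of utility source.

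**Working it through.** **1. Reproduce the plan's expected gain (Part 2, section 2).** Inputs: 199 and 65 interval cancers per round, 5-year survival of 95% and 78%, 27 years of remaining life, 45,000 women.

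- Deaths averted: (199 − 65) × (0.95 − 0.78) = 134 × 0.17 = 22.8, rounded to 23.
- Life-years: 23 × 27 = 621. This matches the plan: "an additional 621 extra life years are gained per round with the proposed population-based screening study".
- Per woman per round: 621 / 45,000 = 0.0138.
- Five two-yearly rounds (years 0, 2, 4, 6, 8): 5 × 0.0138 = 0.069.

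These life-years are valued at full health and undiscounted.

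**2. Break-even source difference.** Let d be the arm I mean EQ-5D minus the population mean, for reasons other than MRI. If each source sets its strategy's utility level for 10 years, the artefact is 10 × d QALY per woman. It equals the expected gain at d = 0.069 / 10 = 0.0069.

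| Assumed d | Artefact (10 × d) | Artefact / 0.069 |
|---|---|---|
| 0.005 | 0.05 | 0.7 |
| 0.01 | 0.10 | 1.4 |
| 0.02 | 0.20 | 2.9 |

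The sign can go either way: d = −0.01 turns 0.069 into 0.069 − 0.10 = −0.031.

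**3. Only life-years inside the 10-year horizon.** Step 1 credits 27 years per averted death, but the model counts 10 years from the start of screening. Deaths averted per woman per round: 23 / 45,000 = 0.000511. The lag from a round to the death averted is an assumption.

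- Lag 5 years: (5 + 3 + 1) × 0.000511 = 0.0046; break-even d = 0.0005.
- Lag 2.5 years: (7.5 + 5.5 + 3.5 + 1.5) × 0.000511 = 0.0092; break-even d = 0.0009.

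**4. Allowing for milder disease.** Assume each of the 134 tumours per round moves from the 25% to the 10% weight (0.15) for 5 years. This adds 5 × 134 × 0.15 × 5 / 45,000 = 0.011. Break-even rises only to (0.069 + 0.011) / 10 = 0.0080.

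**5. What could produce a d of this order (all gaps assumed).**

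- Willingness: with 34% not scanned, a gap of 0.02 between acceptors and decliners puts acceptors 0.34 × 0.02 = 0.0068 above the whole-arm mean.
- MRI exclusions: if 1% to 2% are barred and score 0.2 lower, the shift is 0.002 to 0.004. That is below 0.0069 but above the in-horizon break-even.
- Age: if the population mean age is 60 to 62.5, the gap from 53 is 7 to 9.5 years. A fall in EQ-5D of 0.0069 / 7 = 0.0010 to 0.0069 / 9.5 = 0.0007 per year of age would be enough.

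**The case against.** The strongest reply is that the plan does not spell out how EQ-5D enters the simulation. It nowhere says that the raw arm I mean becomes the utility of every simulated woman in the MRI strategy for 10 years. If the analysts intend one baseline for both strategies and use arm I scores only for change around the MRI, the artefact is zero. This stands as a limit on certainty. However, the plan names a separate source for the control group, so the straightforward reading is two levels, and a different intention has to be written down.

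A reader might also infer that only women who agreed to the scan complete EQ-5D. The documents make that probable but do not establish it: the quality-of-life section refers to the whole intervention arm, and the flowchart is not shown. If every invited woman were surveyed, the selection part would shrink, but the mismatch of source and age would remain.

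The age argument is the softer one. Both sources cover the same nominal range, the model takes in demographic data of the study population, and age-specific population values may be available. The plan simply does not say that they will be used.

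Finally, controls cannot be contacted without giving up the pre-randomisation design, so external values for them are an understandable choice. That explains the population source for controls, but not a different source for the MRI strategy.

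**Conclusion.** The point holds as a conditional one. As written, the cost-per-QALY comparison draws its two utility levels from different populations, and nothing visible removes differences that MRI did not cause. The expected gain is so small that a difference of about 0.007 in mean EQ-5D held for 10 years would match all of it. Under the assumed lags, 0.0005 to 0.0009 would do so if only in-horizon life-years count.

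This rests on the two-level reading of section 9, on the difference persisting for 10 years, and on the gain in Part 2. Every value of d used here is an assumption.

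It is tempting to conclude that the ICER will be biased in favour of MRI, or to state by what percentage it will be wrong. The documents support neither. They contain no EQ-5D values, so the sign is unknown. A percentage based on 0.069 would also mix 27 years of survival per averted death with a 10-year model.

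Nor do the MRI exclusions and refusals threaten the primary outcome. The intention-to-treat rule keeps those women in arm I for the interval cancer comparison. The cost per life-year gained does not use EQ-5D and is likewise unaffected.

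**What to change.** Amend Analysis of cost-effectiveness in Part 7, section 9, to state that:

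1. both simulated strategies use one baseline EQ-5D source, matched to the age of the simulated women;
2. the effect of MRI on quality of life enters only as within-woman change among scanned women, taken from the trial questionnaires if the schedule includes a measurement before the MRI;
3. the 10%, 25% and 40% tumour reductions apply identically to both strategies;
4. a sensitivity analysis varies the baseline source.

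The price is that the directly measured arm I utility level no longer feeds the ICER; measured change after MRI still can. No extra women, scans or questionnaires are needed, and there is no contact with controls, so the pre-randomisation design is kept. The eligibility and randomisation sections need no change for this purpose.
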